1.5.2 Power analysis

Using data from a previous study with multifocal contact lenses, minimum intra-subject standard deviation values on a 0-100 scale for comfort, distance vision, near vision and overall score were 18, 16, 19 and 17 units, respectively. Assuming a meaningful difference of 10 units and an alpha of 0.05, data from 30 subjects are required to provide power of 0.80 or greater for equivalence testing for these four parameters. To allow for ineligible subjects and discontinuations, up to 40 subjects will be recruited.

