Visit 1	
Informed consent Explanation of study procedures and subject instructions Ocular, medical and contact lens histories
 
[REDACTED]
 
[REDACTED]
 
Inclusion/exclusion criteria confirmed Proclear MFT fitted (from fitting bank) 15 minutes after application:
 
[REDACTED]
 
Determination of ideal contact lens specification Proclear MFT removed and Biofinity TMF applied (from fitting bank) 15 minutes after application:
 
[REDACTED]
 
Determination of ideal contact lens specification Study lenses ordered
 
Changes to general and ocular health and medications
 
[REDACTED]
 
Proclear MFT applied 1 minute after application:
 
[REDACTED]
 
[REDACTED]
 
Lenses removed Biofinity TMF applied
 
[REDACTED]
 
[REDACTED]

Visit 2	

	Lenses removed [REDACTED]	
	Payment processed	

Table 1: Study summary.

Section 1. Overview

1.1 **Background**

This project seeks to compare the clinical performance of the Proclear Multifocal Toric and Biofinity Toric Multifocal soft contact lenses.

1.2 **Personnel**

This work will be conducted at Eurolens Research, The University of Manchester under the general direction of [name] PhD MCOptom FAAO FBCLA. The Principal Investigator for the work is [name] PhD MCOptom FAAO FBCLA.

1.3 **Study objectives**

This study aims to compare the short-term clinical performance of the two study contact lenses.

1.4 **Study design**

This will be a subject-masked, bilateral study, controlled by cross-comparison. Up to 40 subjects will wear the Proclear Multifocal Toric and the Biofinity Toric Multifocal lens in the clinic only, following an initial visit to determine ideal lens specifications.

1.5 **Statistical considerations**

The principal hypothesis to be tested in this work is that subjective scores for the lenses will be substantially equivalent. The primary outcome variable is subjective distance vision.

[REDACTED]
[REDACTED] As such, these will be compared using linear regression models or other parametric methods. [REDACTED]

[REDACTED]
[REDACTED] Deviations from this plan will be discussed in the final report. Deviations may be necessary due to differences between the actual data distribution compared with the anticipated data distribution.

1.5.1 **Missing, unused and spurious data**

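### The power calculation uses the lowest SDs from the previous study, so the stated power at 30 completers is optimistic with respect to SD; on distance vision it falls below 0.80 once the SD passes about 18.3.

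*Combined protocol and SAP*

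**What the plan says.** Section 1.5 of the combined protocol and SAP sets an equivalence objective: "The principal hypothesis to be tested in this work is that subjective scores for the lenses will be substantially equivalent". It adds: "The primary outcome variable is subjective distance vision".

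Section 1.5.2 gives the planning inputs. They are drawn from an earlier multifocal lens study and described as "minimum intra-subject standard deviation values on a 0-100 scale for comfort, distance vision, near vision and overall score". The values are 18 for comfort, 16 for distance vision, 19 for near vision and 17 for overall score. The other inputs are given as "Assuming a meaningful difference of 10 units and an alpha of 0.05". The conclusion is that "data from 30 subjects are required to provide power of 0.80 or greater for equivalence testing for these four parameters". The margin between 30 and 40 subjects has its own stated purpose: "To allow for ineligible subjects and discontinuations, up to 40 subjects will be recruited".

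The section gives no average, pooled or largest SD from the earlier study, does not say what the minimum was taken over, and shows no power at any other SD.

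**The concern.** With sample size, margin and alpha fixed, the power of an equivalence test falls as the SD rises. Taking the smallest of several SD estimates therefore pushes the calculated power upwards. It does so for all four scores, including the primary. The ten extra recruits are assigned to ineligibility and drop-out, so nothing in the plan is set aside for a larger SD.

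What is at stake is the chance of an inconclusive result when the two lenses really are equivalent. If the SD for distance vision is nearer 20 than 16, that chance at 30 completers is about 30% (1 − 0.697), compared with 9% (1 − 0.910) at the planning value. The sponsor and the ethics committee cannot see this from section 1.5.2.

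**Working it through.** **Inputs from the documents.** SDs 18, 16, 19 and 17; difference of 10 units; alpha 0.05; 30 completers (all from section 1.5.2). Distance vision is primary (section 1.5). Every subject wears both lenses, so the analysis is taken as paired, with n − 1 degrees of freedom.

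**Assumptions where the documents are silent.** The SDs are SDs of the within-subject lens difference, the 10 units are an equivalence margin of ±10, alpha is 0.05 for each of two one-sided tests, and the true difference is 0.

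**Step 1: reproduce the plan's figure.** By normal approximation, power = 2Φ(10 / (SD/√n) − 1.645) − 1.

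- SD 16, n = 30: standard error 16/√30 = 2.921; 10/2.921 = 3.423; 3.423 − 1.645 = 1.778; power 0.925.
- SD 19, n = 30: standard error 19/√30 = 3.469; 10/3.469 = 2.883; 2.883 − 1.645 = 1.238; power 0.784.

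SDs 17 and 18 give 0.885 and 0.838. The largest SD, 19, drives the sample size and needs 31 subjects on this formula. The plan's 30 is thus reproduced to within one subject and two points of power.

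**Step 2: exact power at the stated SDs.** This uses the t distribution with n − 1 degrees of freedom, integrated over the sampling distribution of the SD.

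| Score | Lowest SD | Power at n = 30 | n needed for 0.80 |
|---|---|---|---|
| Distance vision (primary) | 16 | 0.910 | 24 |
| Overall | 17 | 0.867 | 27 |
| Comfort | 18 | 0.815 | 30 |
| Near vision | 19 | 0.758 | 33 |

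**Step 3: how far the SD can rise.** At n = 30, exact power equals 0.80 at SD 18.27. For distance vision that is 18.27/16 − 1 = 14% above the planning value. For comfort it is 18.27/18 − 1 = 1.5%. For near vision the planning value of 19 is already past it.

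| SD for distance vision | Power, n = 30 |
|---|---|
| 16 | 0.910 |
| 17.6 (+10%) | 0.84 |
| 18.4 (+15%) | 0.79 |
| 19.2 (+20%) | 0.75 |
| 20 (+25%) | 0.70 |

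If every SD is 15% above its minimum, power for comfort, distance, near and overall is 0.65, 0.79, 0.58 and 0.72. At 25% above, it is 0.54, 0.70, 0.46 and 0.62. These percentages are illustrative, because the documents give no other SD.

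**Step 4: more completers.** The SD at which power equals 0.80 is 19.8 (24% above 16) with 35 completers and 21.2 (33% above 16) with 40. At SD 20, power is 0.70, 0.79 and 0.86 with 30, 35 and 40 completers.

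**Step 5: sensitivity to the assumptions.** By normal approximation the n = 30 crossing point is SD 18.7 (17% above 16). With alpha 0.025 per side, power at SD 16 is 0.822 and the crossing point is SD 16.3 (2% above). With a true difference of 2 or 3 units, power at SD 16 is 0.84 or 0.75. If the stated value is a within-subject SD instead, the SD of the difference is √2 × 16 = 22.6 and power is 0.53.

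**The case against.** The strongest reply is that the size of the problem cannot be learned from the documents. Section 1.5.2 gives one SD per score and no spread. The next value in the earlier study might be barely above 16 or well above it. This stands: what the documents show is an optimistic input and no sensitivity range.

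Four further points also stand.

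- A reader might infer that the stated power is an upper limit. It is not. The earlier study is described only as one of multifocal lenses, whereas this trial scores toric multifocals after about 15 minutes' adaptation per lens in the clinic. Its SD could fall below 16 as well as above it.
- A reader might take the words after 0.80 in the power statement as promising a floor whatever the SD. With one sample size quoted for four scores, they more naturally mean at least 0.80 for each score at the listed SDs.
- Thirty completers is not the most favourable case. The study summary treats 30 as the least number to complete, from up to 40 consented, and Step 4 shows how far extra completers move the crossing point. They are not guaranteed, though, and the power claim itself is made at 30.
- The plan's sum reproduces closely, so this is a choice of input and not an arithmetical mistake.

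It is also fair that the primary is planned with some reserve, at about 0.91, and that any calculation crosses 0.80 at some SD. That does not answer the concern for comfort and near vision, which are covered by the same power statement and have little or no reserve even at their lowest SDs.

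**Conclusion.** The point holds as a matter of planning input. The power stated for 30 completers rests on the lowest SDs of the earlier study and is optimistic in that respect. Under the assumptions listed in the working, the primary has room for an SD about 14% above 16. Comfort has room for about 1.5%, and near vision is below 0.80 at its own planning value.

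It would be tempting to conclude that the primary comparison is underpowered, or that it looks adequate only because the lowest SD was chosen. The documents support neither, since the earlier study's typical SD is not given. The figures above are a range of consequences and not a demonstrated shortfall on distance vision. Of the favourable assumptions, the reading of the SDs as SDs of paired differences, the 0.05 per one-sided test and the zero true difference matter most; relaxing any of them lowers the figures.

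**What to change.** In section 1.5.2, replace the minimum SDs with a representative SD from the same previous study, for example the SD pooled over its comparisons. Restate power at 30 completers for distance vision and for each of the other three scores. Keep the claim of at least 0.80 only for the scores where that SD supports it.

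If the minimum values are kept, say that the power is based on the lowest SDs, and show it beside the power at the pooled and largest SDs.

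The cost is one recalculation from the study the planners already drew on, and a change of wording. The stated power may become less favourable. The restatement itself needs no extra subjects.

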Clinical investigation plan

**C24-750
(EX-MKTG-159)**

A clinical comparison of two multifocal toric soft contact lenses

[figure not shown]
**A clinical evaluation for
CooperVision Inc**

**Principal Investigator
[name]**

March 2024

Contents

Document control	3
Study summary	
Section 1. Overview	6
1.1 Background	6
1.2 Personnel	6
1.3 Study objectives	6
1.4 Study design	6
1.5 Statistical considerations	6
1.6 Risk analysis	7
1.7 Clinical trial registration	7
Section 2. Resources	8
2.1 Subject selection	8
2.2 Subject discontinuation	9
2.3 Safety parameters, adverse events and concurrent illnesses	9
2.4 Study termination	10
2.5 Protocol deviations	10
2.6 Study resources	10
2.7 Study control	11
2.8 Documentation	11
2.9 Data collection and analysis	12
2.10 Study completion	12
2.11 Subject confidentiality	12
2.12 Study monitoring	12
Section 3. Subject management	13
3.1 Visit scheduling	13
3.2 Visit conduct	13
3.3 Monitoring subject compliance	17
Section 4. Study co-ordination	18
4.1 Document processing	18
4.2 Disclosure	18
4.3 Personnel	18

Study summary

This subject-masked bilateral non-dispensing crossover study will compare the clinical performance and subjective acceptance of the Proclear Multifocal Toric and Biofinity Toric Multifocal soft contact lenses.

Up to 40 subjects will be consented with the aim of completing at least 30 subjects. Each subject will attend an initial visit at which the ideal lens specifications for each lens brand will be determined and ordered. At the second visit, all subjects will be fitted with the Proclear Multifocal Toric lens first followed by the Biofinity Toric Multifocal lens. [REDACTED]

[REDACTED]

A study summary is shown in Table 1.

Visit	Procedures

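### Power of 0.80 or greater at 30 subjects is claimed for all four scores, but near vision reaches only about 0.76 even on the favourable reading of the SDs, and the type of SD is not defined

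*Combined protocol and SAP*

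**What the plan says.** The principal hypothesis in section 1.5 is one of equivalence between the two lenses, and "The primary outcome variable is subjective distance vision".

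Section 1.5.2 takes its SDs from an earlier multifocal lens study. It describes them as "minimum intra-subject standard deviation values on a 0-100 scale", and the values for "comfort, distance vision, near vision and overall score were 18, 16, 19 and 17 units, respectively". The remaining inputs are given as "Assuming a meaningful difference of 10 units and an alpha of 0.05". From these it concludes that "data from 30 subjects are required to provide power of 0.80 or greater for equivalence testing for these four parameters".

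On numbers, section 1.5.2 adds: "To allow for ineligible subjects and discontinuations, up to 40 subjects will be recruited". The Study summary puts it as "Up to 40 subjects will be consented with the aim of completing at least 30 subjects", while section 2.1 gives 30 completers simply as the aim.

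The analysis text in section 1.5 is partly redacted. What can be read is "As such, these will be compared using linear regression models or other parametric methods". No redaction is marked within section 1.5.2.

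**The concern.** The power claim covers four named scores, so it is wrong as written if any one of them falls below 0.80. Near vision has the largest SD and sets the limit.

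Three inputs that an equivalence calculation needs are also missing: whether an intra-subject SD means the SD of paired differences or the within-subject SD of a single score, whether alpha is 0.05 per one-sided test, and what true difference is assumed. The first matters most. For two measurements with independent within-subject errors, the SD of the difference is √2 times the within-subject SD, and that decides whether 30 completers are ample or far too few for the primary outcome. Calling the SDs minimum values adds a further doubt: if they are the smallest seen in the earlier study, every power derived from them is a best case.

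**Working it through.** **Inputs from section 1.5.2:** SDs of 16 (distance), 17 (overall), 18 (comfort) and 19 (near); difference of 10 units; alpha 0.05; n = 30; target power 0.80.

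**Assumptions, because the plan is silent:** equivalence margin ±10; two one-sided tests (TOST) at 0.05 each; true difference 0, the most favourable value; one score per lens per subject; SDs are of paired differences. All subjects wear the lenses in the same order, so a simple paired test has n − 1 = 29 degrees of freedom.

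**1. Attempt to reproduce the plan's figure (normal approximation).**

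Power = 2Φ(10√n / SD − 1.645) − 1.

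Near vision: 10 × 5.477 / 19 = 2.883; 2.883 − 1.645 = 1.238; Φ(1.238) = 0.892; power = 2 × 0.892 − 1 = 0.784. The smallest n giving 0.80 is 31. This comes close to the plan's 30 but stays below its floor.

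**2. Exact calculation.**

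Equivalence is concluded when |mean difference| + t × s/√n < 10, with t = 1.699 on 29 df. Power is the probability of that event, integrated over the chi-square distribution of the sample variance s².

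| Score | SD | Approx. power, n = 30 | Exact power, n = 30 | Exact n for 0.80 |
|---|---|---|---|---|
| Distance (primary) | 16 | 0.925 | 0.910 | 24 |
| Overall | 17 | 0.885 | 0.867 | 27 |
| Comfort | 18 | 0.838 | 0.815 | 30 |
| Near | 19 | 0.784 | 0.758 | 33 |

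Simulation with 1,000,000 runs gives 0.759 for near vision.

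**3. Rounding of the SDs.** A printed 19 may stand for 18.5 to 19.5.

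| Near-vision SD | Exact power | Approx. power | n for 0.80 (exact / approx.) |
|---|---|---|---|
| 18.5 | 0.787 | 0.812 | 31 / 30 |
| 19.0 | 0.758 | 0.784 | 33 / 31 |
| 19.5 | 0.728 | 0.756 | 34 / 33 |

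The largest SD that gives 0.80 at n = 30 is 18.27 by the exact test and 18.72 by the approximation. Exact power for near vision is therefore below 0.80 over the whole rounding range. Comfort keeps 0.80 exactly only if its unrounded SD is 18.27 or less.

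**4. The other unstated inputs** (exact, n = 30, paired-difference SDs).

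| Change | Distance | Overall | Comfort | Near |
|---|---|---|---|---|
| True difference 1 unit | 0.892 | 0.847 | 0.796 | 0.739 |
| True difference 2 units | 0.839 | 0.792 | 0.740 | 0.686 |
| Alpha 0.025 per side | 0.822 | 0.751 | 0.673 | 0.591 |

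**5. If the SDs are within-subject SDs of single scores.** SD of differences = √2 × SD, which gives 22.63, 24.04, 25.46 and 26.87.

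| Score | Exact power, n = 30 | Exact power, n = 40 | Exact n for 0.80 |
|---|---|---|---|
| Distance (primary) | 0.53 | 0.73 | 46 |
| Overall | 0.44 | 0.65 | 51 |
| Comfort | 0.35 | 0.57 | 57 |
| Near | 0.28 | 0.50 | 64 |

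**6. A possible origin of the figure.** A two-sided paired t-test to detect a 10-unit difference at SD 19 and n = 30 has power 0.796, which rounds to 0.80. That is a difference test, not an equivalence test. It is a reason to check the original calculation, not evidence of what was done.

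**The case against.** The strongest reply is that the demonstrated error is small and may be only rounding. The section names no calculation method, so the exact test is a choice made here. With the normal approximation and an unrounded near-vision SD of about 18.7 or less, 30 subjects do give 0.80. Near vision is not the primary outcome, and on the same reading distance vision has power of 0.91. More than 30 subjects may also complete.

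Much of this stands, and it is why the point is minor. It does not rescue the sentence: at the printed SD of 19 neither method reaches 0.80, and the claim is made at 30. The cap of 40 leaves room for more completers, but nothing commits the study to obtaining them.

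The second reply is that the plan's own numbers favour the paired-difference reading. That reading needs 31 to 33 completers for the limiting score, close to the stated 30, whereas the single-score reading needs 46 to 64. This is a fair inference, and the 0.53 for distance vision must be read as conditional. It is not proof, because the section does not define the SD and the earlier study is not available to the reader.

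Third, the redactions in section 1.5 may hide a different model and error term. The finding is therefore confined to a simple paired equivalence test.

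**Conclusion.** The concern holds, at minor severity. The claimed floor of 0.80 is not met for near vision. At the printed SD of 19, power at 30 completers is 0.758 (exact) or 0.784 (approximation), so the shortfall is 0.80 − 0.758 = 0.042 or 0.80 − 0.784 = 0.016, equivalent to 1 to 3 more completers. Across the rounding range it runs from none (approximation, SD 18.5) to about 7 points (exact, SD 19.5). The other three scores meet 0.80, but only with paired-difference SDs, alpha 0.05 per side and a true difference close to 0.

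Confidence is high for the near-vision arithmetic. The point about the primary outcome is conditional: the text does not let a reader establish whether power for distance vision is about 0.91 or about 0.53, although the stated sample size sits closer to the first.

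**What to change.** First confirm from the earlier study whether 16, 17, 18 and 19 are SDs of paired lens differences, and whether minimum means the smallest values observed. Then replace the blanket claim in section 1.5.2 with a power for each score at 30 completers, stating the SD type, alpha per side and assumed true difference.

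If paired differences are confirmed, suitable wording would be:

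> With SDs of paired lens differences of 16, 17, 18 and 19, a margin of ±10, alpha of 0.05 per one-sided test and a true difference of 0, 30 completers give power of about 0.91 for distance vision (primary), 0.87 for overall score, 0.82 for comfort and 0.76 for near vision.

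The cost is one check of the earlier data, one reworded paragraph and a slightly less favourable figure for near vision. No change to the enrolment cap is needed: the 31 to 34 completers that would bring near vision to 0.80 by the exact test, depending on rounding, fit under 40.

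If the values prove to be within-subject SDs of single scores, the paragraph should state 0.53, 0.44, 0.35 and 0.28 in the same order, and the sample-size justification must be re-examined. The 46 to 64 completers then needed exceed the cap of 40, so the cost on that branch is not merely editorial.

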1.6 Risk analysis

This study is considered to be a non-significant risk study based on United States Food and Drug Administration (FDA) and International Standards Organisation (ISO) guidelines due to the daily wear nature of the study. The work where practical will be conducted in accordance with:

- ICH Good Clinical Practice Guidelines
- BS EN ISO 14155 'Clinical investigation of medical devices for human subjects - Good clinical practice'
- Declaration of Helsinki

With the potential benefit of this study, the work is considered to be ethically justifiable. Ethical approval will be sought from the University of Manchester Senate Committee on the Ethics of Research on Human Beings (hereafter referred to as Manchester UREC).

1.7 Clinical trial registration

This study will be registered with clinicaltrials.gov in accordance with section 801 of the Food and Drug Administration (FDA) Act which mandates the registration of certain clinical trials of drugs and medical devices.

Section 2. Resources

2.1 Subject selection

In this work, up to 40 subjects will be consented with the aim of 30 subjects completing the study.

2.1.1 Subject withdrawal and replacement

This study includes two clinical visits. Once the study consent form is signed, the subject is considered to be enrolled on the study. Subjects who have signed the consent form, but who have not completed the initial visit will usually be replaced. All subject data will be included in the final analyses unless there are strong grounds for exclusion; such grounds will be detailed in the final report.

2.1.2 Subject recruitment

Subjects will be recruited by one or more of following means:

1. Posting study details on The University of Manchester's 'Research Volunteers' website.
2. Correspondence to existing wearers on the Eurolens Research database of subjects.
3. Advertising through a variety of media via a format separately approved by Manchester UREC.

2.1.3 Inclusion criteria

Subjects will only be eligible for the study if:

1. They are aged 35 years or over and have capacity to volunteer.
2. They understand their rights as a subject and are willing to sign a Statement of Informed Consent.
3. They are willing and able to follow the protocol.
4. They agree not to participate in other clinical research for the duration of this study.
5. They are currently wearing soft contact lenses or have done so within the past 12 months.
6. They have a spherical prescription between +10.00 and -10.00DS inclusive, (based on the ocular refraction).
7. They have astigmatism of between -0.75 and -5.75DC (based on the ocular refraction) in each eye.
8. They have a reading addition component to their spectacle refraction of between +0.75 and +2.50DS.
9. They can be satisfactorily fitted with the study lenses.
10. They own a wearable pair of spectacles.

2.1.4 **Exclusion criteria**

Subjects will not be eligible to take part in the study if:

1. They have an ocular disorder which would normally contraindicate contact lens wear.
2. They have a systemic disorder which would normally contra-indicate contact lens wear.
3. They are using any topical medications such as eye drops or ointment.
4. They have had cataract surgery.
5. They have had corneal refractive surgery.
6. They have any corneal distortion resulting from previous hard or rigid lens wear or have keratoconus
7. They have any ocular abnormality which would, in the opinion of the investigator, normally contraindicate contact lens wear.
8. They have eye or health conditions including immunosuppressive or infectious diseases which would, in the opinion of the investigator, contraindicate contact lens wear or pose a risk to study personnel; or a history of anaphylaxis or severe allergic reaction.
9. They have taken part in any other contact lens or care solution clinical trial or research, within two weeks prior to starting this study.

2.2 **Subject discontinuation**

In general, subjects should be discontinued at any time, if it is in their best interests, as judged by the investigator. Reasons for this may include clinical signs of grade 3 or more, lack of motivation, discomfort, repeated refusal to follow instructions or the use of non-study products such as solutions or lenses. Subjects will be discontinued if a serious adverse event occurs or if they miss two or more planned consecutive visits. Subjects who fail to satisfy all the inclusion and exclusion criteria will be discontinued and replaced. Subjects who choose to leave the study at their own request will be replaced. All discontinuations will be carefully recorded.

2.3 **Safety parameters, adverse events and concurrent illnesses**

The key safety parameters are the serious and significant ocular adverse events listed in

Clinical assessment is made at the study visit(s) for these parameters. The presence of an adverse event will be reported on the case report forms and those described as 'serious' or 'significant' will be detailed in the final report. Similarly, any concurrent illness that is likely to impact on the relevance and quality of the captured data will be noted on the case report form.

2.3.1 **Investigator responsibilities**

The investigator will be appropriately qualified, have suitable resources to conduct the study, have study training, ensure subject safety and data integrity. At all times they will act in the best interest of the subject. Referral or treatment of an adverse event or other clinical finding should be initiated in the best clinical judgement of the investigator, irrespective of their participation in the clinical study.

2.3.2 **Investigator reporting responsibilities**

In the case of a 'serious' or 'significant' adverse event, the Principal Investigator will notify the Sponsor as soon as possible. Manchester UREC and any regulatory authorities will be informed as required.

2.4 **Study termination**

If it becomes necessary to terminate the study earlier than planned, the Sponsor will notify the Principal Investigator who will end the study with the cooperation of other staff members. Manchester UREC will be informed.

2.5 **Protocol deviations**

These are unanticipated or unintentional changes that occur after Manchester UREC approval. Any deviations, major (affect the integrity of the study and/or subject safety) or minor from this protocol will be recorded, and reported to the Sponsor as appropriate. Manchester UREC will be informed as necessary.

2.5.1 **Protocol amendments**

Amendments will be agreed between the Sponsor and the Principal Investigator with the cooperation of other staff members. Amendments will be recorded, identified and distributed. Approval from Manchester UREC will be obtained as necessary.

2.6 **Study resources**

Study products will be stored according to the manufacturer's product instructions.

2.6.1 **Lenses**

Details of the study lens are provided in Table 2. All lens types are CE marked. Initial lens selection will be as indicated by the manufacturer fitting guidelines.

	First lens	Second lens
Lens name	Proclear Multifocal Toric	Biofinity Toric Multifocal
Manufacturer	CooperVision	CooperVision
Material	Omafilcon A	Comfilcon A
EWC (%)	59	48
BOZR (mm)	8.8	8.7
Diameter (mm)	14.4	14.5
Spherical powers (D)	+10.00 to -10.00 (0.50D steps after -6.50)	-10.00 to -6.50(0.50 steps) -6.00 to +6.00 (0.25 steps)

Cylinder powers (D)	-0.75 to -5.75	+6.50 to +10.00 (0.50 steps)
Axes (degrees)	5 to 180 (5 degree steps)	-0.75 to -5.75 5 to 180 (5 degree steps)
Add (D)	+1.00 to +4.00	+1.00 to +2.50
Multifocal design	Centre distance (D) and centre near (N)	Centre distance (D) and centre near (N)

Table 2: Study lenses.

